5.3 Study Restrictions

Each subject will be questioned on the specific points listed below prior to drug administration. If a subject admits a non-compliance with these restrictions, the Principal Investigator (or designee) and/or the sponsor will decide whether or not the subject will be permitted to remain in the study. Non-compliance with these restrictions will be recorded.

- Subjects will be instructed to abstain from planning a trip to sunny climate or use of tanning equipment between screening and follow-up visits.
- Subjects will be instructed to abstain from using any drugs/treatments that may influence atopic dermatitis (refer to exclusion criteria and prohibited therapies or procedures section) throughout the study.
- Subjects will be required to start fasting at least 8 hours before drug administration upon waking. Fasting will continue for at least 60 minutes following drug administration, after which subject can have breakfast. Water will be allowed at all times during the fasting period, but no other fluids will be permitted. Medication(s) for other conditions that are permitted in the study can be taken as usual.
- For Baseline (Day 0), week 4 and week 8 visits, a blood draw will be performed for PK analysis. PK samples must be taken pre-dose; therefore, study drug administration will occur during the visit for Day 0 and week 4 visits. Because dosing will occur at the clinic on Day 0 and week 4, subjects will be required to fast for at least 8 hours prior to study drug administration and will be allowed to have a meal 60 minutes after study drug administration.

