5.4 Discontinuations

Subjects have the right to withdraw from the study at any time for any reason without penalty. The investigator also has the right to withdraw subjects from the study if he feels it is in the best interest of the subject or if the subject is uncooperative or non-compliant. It is understood by all concerned that an excessive rate of withdrawal can render the study un-interpretable; therefore, unnecessary withdrawal of subjects should be avoided. Should a subject decide to withdraw, all efforts will be made to complete and report the observations, particularly the follow-up examination, as thoroughly as possible.

The investigator or one of his or her staff members should contact the subject either by telephone or through a personal visit to determine as completely as possible the reason for the withdrawal, and record the reason in subject's source document and CRF. A complete final early termination (week 8) evaluation at the time of the subject's withdrawal should be made with an explanation of why the subject is withdrawing from the study. If the reason for removal of a subject is an adverse event or an abnormal laboratory test result, the principal specific event or test will be recorded. Subjects who discontinue the study before week 8 visit will be asked to come for an early termination visit as soon as possible and have the assessments listed at week 8 performed. They will also be asked to return two weeks later for the safety assessments listed at

week 10.

Reasons for discontinuation include:

- The investigator decides that the subject should be withdrawn. If this decision is made because of a serious or persistent adverse event, laboratory abnormality, or intercurrent illness, the study drug is to be discontinued and appropriate measures are to be taken. The investigator will notify the Sponsor or designee immediately.
- The subject or attending physician requests that the subject be withdrawn from the study.
- The subject for any reason requires treatment with another therapeutic agent that has been demonstrated to be effective for treatment of the study indication. In this case, discontinuation from the study occurs immediately upon introduction of the new agent.
- The subject is lost to follow-up, in this case, a reasonable attempt to contact the subject and ascertain his/her status must be made and these attempts must be documented.
- Serious protocol violation, including persistent non-compliance.

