3.4.3.5 Total and Free DGLA plasma levels, Total Fatty Profile and Interleukins levels

Total DGLA and free DGLA trough plasma levels will be measured at Baseline, week 4 and week 8. Total fatty profiles and interleukins levels will not be covered in this SAP.

4 Sample Size

The primary endpoint can be translated as a responder analysis where a subject will be classified as Responder if he/she achieves an IGA score of 0 (clear) or 1 (almost clear) at Week 8, considering a 2-point decrease from baseline. A sample size of 45 subjects will have a power of 80% to detect a statistically significant difference of 25% between responders from treated group and from the placebo group, based on a chi-square test and an alpha of 0.05. Based on the literature review, it is expected that the placebo could reach up to 7%, so the minimal proportion expected in the treated group should be at least 32%. Allowing for 10% drop-out, a total of 100 subjects should be enrolled in the study.

5 General Considerations

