5.5 Multiple Testing

Since there are only 2 treatment groups involved in this study, no correction for multiplicity will be performed.

6 Summary of Study Data

All continuous variables will be summarised using the following descriptive statistics: n (non-missing sample size), mean, standard deviation (SD), median, inter-quartile range (25th and 75th percentiles), maximum, and minimum. The frequency and percentages (based on the non-missing sample size) of observed levels will be reported for all categorical measures.

In general, all data will be listed, sorted by treatment group, site and subject, and when appropriate by visit number within subject. All summary tables will be structured with a column for each treatment in the same order (DS107G, Placebo) and will be annotated with the total population size relevant to that table/treatment.

Day 0 is the first day of study medication. In the event that there is more than one value for a given assessment prior to the study drug start date, the value obtained closest to Day 0, before administration of study drug will be considered as the baseline value. The baseline value will be the value nearest to and before the first dose of the study medication.

All statistical tests will be two-sided and will be performed with a significant level of 0.05, unless otherwise specified.

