6.2 Protocol Deviations

Protocol deviations may include, but are not limited to:

- Visit outside of the visit window
- Missed visit
- Missed/Extra dose(s)
- Study Procedure(s) not done
- Prohibited medication
- Etc.

A listing of all protocol deviations will be presented and documented in the study file. A descriptive summary table of protocol deviation categories by treatment group will be presented.

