7.1 Primary Efficacy Analysis

The primary endpoint can be translated as a responder analysis where a subject will be classified as Responder if he/she achieves an IGA score of 0 (clear) or 1 (almost clear) at Week 8, considering a 2-point decrease from baseline. Patients who did not complete the study (i.e. subjects with an early termination visit at Week 8) will be classified as non-responder.

The comparison between groups for the primary endpoint will be done using a Cochran-Mantel-Haenszel (CMH) test where the site will be used as the stratification factor. A sensitivity analysis will also be conducted using a Fisher's exact without Site. Subgroup analyses will also be performed on responders vs. non responders (using CMH test stratified for site) for each subgroup of patients (Very Severe/Severe and Moderate), separately.

The primary efficacy analysis will be done using observed values. A supportive analysis will be conducted using the LOCF method. For subjects who did not complete the study, the last non-missing IGA results (including results collected during the early termination Week 8 visit) will be used.

The analyses will be done using the ITT population and will serve as the primary analysis while the analysis of the primary endpoint using the PP population will be used as a supportive analysis.

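### Users of prohibited therapy who stay to Week 8 can count as primary responders, while subjects withdrawn for an effective agent are non-responders; LOCF may also use IGA scores taken after such use

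*SAP*

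**What the plan says.** **Primary analysis.** SAP 7.1 states "The primary efficacy analysis will be done using observed values", in the ITT population, which SAP 5.2.1 defines as everyone randomised. The same section makes subjects who did not complete the study non-responders.

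**LOCF.** The supportive analysis in SAP 7.1 uses the last non-missing IGA of a non-completer, "including results collected during the early termination Week 8 visit". SAP 5.3 adds nothing on scores taken after other treatment has started.

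**Leaving for another agent.** Under protocol 5.4, when a subject needs another agent of demonstrated efficacy in the indication, "discontinuation from the study occurs immediately upon introduction of the new agent". The Week 8 assessments are then done at an early-termination visit, as soon as that can be arranged.

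**Staying after a breach.** Protocol 5.3 lists abstaining from treatments that may influence atopic dermatitis among the study restrictions. If a subject admits a breach, the investigator and/or the sponsor "will decide whether or not the subject will be permitted to remain in the study".

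**How the SAP records it.** SAP 6.2 names "Prohibited medication" as an example of a protocol deviation. SAP 5.2.3 removes subjects from the per-protocol set if the deviation is judged significant in a blinded review before database lock.

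**The concern.** The plan treats rescue as failure when it leads to withdrawal but has no rule for the same kind of event when the subject stays. A subject who used a prohibited topical product, was kept in the study and was clear at Week 8 is a responder. Another who started an effective agent and was withdrawn is a non-responder. What separates them may be a case-by-case decision about continuation, which is not a property of the disease or the treatment.

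At stake is what the Week 8 responder rate measures. Clearance produced by another therapy would be credited to the randomised arm, and the direction of the bias depends on which arm uses more of it. The LOCF analysis, which is the only planned check on missing primary data, could reverse the primary classification of a rescued subject because of the rescue itself.

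**Working it through.** **1. Follow three subjects through the rules.**

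| Subject | Route | Primary ITT | LOCF |
|---|---|---|---|
| A: starts an effective agent, withdrawn | Protocol 5.4, then SAP 7.1 | Non-responder | Last IGA, which may be the early-termination score taken after the agent started |
| B: uses prohibited therapy, kept in the study, attends Week 8 | Protocol 5.3, SAP 6.2, SAP 7.1 | Observed Week 8 IGA | Observed Week 8 IGA |
| C: as B, but use first disclosed at Week 8 | As B; treatment already completed | Observed Week 8 IGA | Observed Week 8 IGA |

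Route C is possible because the flow chart has no visit between Weeks 4 and 8. The prohibited list in protocol 6.3.2 (including bleach, antimicrobials, and urea or ceramide products) is also wider than the trigger in protocol 5.4, which is limited to agents of demonstrated efficacy.

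**2. Reproduce the plan's sample size.** SAP 4 says "A sample size of 45 subjects will have a power of 80% to detect a statistically significant difference of 25" percentage points, "based on a chi-square test and an alpha of 0.05", with 7% on placebo and 32% on active. SAP 6 makes tests two-sided. I read 45 as per group, since 2 × 45 = 90 and 90 / 0.9 = 100, the stated total.

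The two-proportion formula gives 39 per group without continuity correction and 46 with it, so the stated 45 agrees to within one subject of the corrected figure. Exact power of Fisher's test at 45 per group is 81.7%.

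Power below is from the uncorrected normal approximation:

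power = Φ{[d√n − 1.96 √(2 p̄(1−p̄))] / √(p₁(1−p₁) + p₂(1−p₂))}

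where d is the difference in rates and p̄ their mean. At n = 45, 7% v 32%: (0.25 × 6.708 − 1.96 × 0.5603) / 0.5317 = 1.089, so power is 86.2%.

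**3. Illustrate the effect.** The documents give neither a rate of use nor a response rate after use. Let u be the proportion who use prohibited therapy and stay, r the proportion of them who meet the responder definition, and p the rate otherwise.

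- Observed-value rule: p(1−u) + u·r
- Non-responder rule: p(1−u)

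Worked case, u = 10% placebo and 5% active, r = 50%. Observed: 0.07 × 0.90 + 0.10 × 0.50 = 11.3%, and 0.32 × 0.95 + 0.05 × 0.50 = 32.9%. Non-responder: 6.3% v 30.4%.

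| Use, placebo / active | r | Observed rates (difference) | Power | Non-responder rates (difference) | Power |
|---|---|---|---|---|---|
| 5% / 5% | 50% | 9.15% v 32.9% (23.75) | 80.0% | 6.65% v 30.4% (23.75) | 83.8% |
| 10% / 5% | 30% | 9.3% v 31.9% (22.6) | 76.4% | 6.3% v 30.4% (24.1) | 85.2% |
| 10% / 5% | 50% | 11.3% v 32.9% (21.6) | 70.1% | 6.3% v 30.4% (24.1) | 85.2% |
| 5% / 10% | 50% | 9.15% v 33.8% (24.65) | 82.4% | 6.65% v 28.8% (22.15) | 79.6% |

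With equal use and equal r, the difference is 0.25(1−u) under both rules. The power loss then comes only from the higher rates in both arms. With more use on placebo the observed difference shrinks; with more use on active it grows.

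**4. Test one assumption.** The formulas let users respond at their arm's average rate had they not used anything. If instead every user would have failed, the observed rate is p + u·r and the non-responder rate is p. The 10% / 5% case with r = 50% becomes 12.0% v 34.5%, power 72.2%, against 7% v 32%, power 86.2%. The size of the effect is similar.

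**The case against.** A reader might infer that the primary analysis takes whatever IGA is observed, rescue or not. The documents do not support that. Protocol 5.4 withdraws a subject on introduction of an effective agent, and SAP 7.1 makes that subject a non-responder. The main rescue route is already handled.

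The two protocol sections can also largely be read together: 5.3 as a general compliance check, 5.4 as the specific rule for agents of demonstrated efficacy. Discretion would then mostly cover lesser breaches. This narrows the overlap but does not remove it. Self-use of a topical corticosteroid by a subject who is not judged to require it falls under 5.3, and the SAP is silent on it.

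The per-protocol set is a fair partial answer. It is reviewed blinded, and the SAP plans per-protocol tables for both the observed and the LOCF responder analyses (14.2.1.1.2 and 14.2.1.1.4). But it is supportive, depends on the deviation being judged significant, and drops users where the plan's own rule for rescued leavers counts them as failures.

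It is also tempting to say that the early-termination IGA always follows rescue. Protocol 5.4 asks for the evaluation at the time of withdrawal or as soon as possible, so it may come before, with or after the first dose. Contamination is possible, not established, and affects only a supportive analysis.

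Finally, using observed values regardless of other treatment is a recognised treatment-policy approach. It would be defensible if applied throughout, but this plan already fails the rescued leavers.

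**Conclusion.** The gap is real but narrow. It covers subjects who use prohibited therapy that can affect atopic dermatitis, remain in the study and attend Week 8, plus a supportive LOCF rule that can admit scores taken after a new agent. It should be closed before database lock.

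Its size cannot be derived from the documents. Under the assumed 5-10% use, the cost ranges from about 4 points of power (equal use) to about 9-15 points (10% placebo, 5% active, 30-50% responding). These are illustrations at 45 per group with an uncorrected test, not predictions. A reader might infer that the plan is biased against DS107G; that follows only if use is heavier on placebo. With the pattern reversed (5% placebo, 10% active, 50% responding) the observed difference is 24.65 points against 22.15, in favour of DS107G.

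**What to change.** In SAP 7.1:

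1. Class as a non-responder any subject who, before the Week 8 IGA, used prohibited therapy judged in the blinded pre-lock review capable of affecting the IGA, whether or not the subject stayed. Keep the observed-value result as a sensitivity analysis. Say explicitly that the observed-value wording applies subject to this rule and to the existing rule for non-completers.
2. In LOCF, carry forward only the last IGA before the first such use.

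The review should set out in advance which agents, durations and timings qualify, so that one trivial use is not failed by default. The sponsor must also reconcile protocol 5.3, which leaves continuation to discretion, with protocol 5.4, which requires immediate discontinuation. That is a clinical matter and no rule is proposed here.

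The cost is small. Protocol 6.3 already collects medication start dates, and SAP 5.2.3 already provides for the blinded review. A few observed responses would become non-responses, and the sensitivity analysis would show how many.

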7.2 Secondary Efficacy Analyses

The second efficacy endpoints are:

- Change from baseline in IGA at week 2, 4, and 8
- Change from baseline in EASI at week 2, 4, and 8
- Change from baseline in POEM at week 2, 4, and 8
- Change from baseline in DLQI at week 2, 4, and 8
- Change from baseline in SCORAD at week 2, 4, and 8
- Change from baseline in VAS at week 2, 4, and 8
- Change from baseline in BSA at week 2, 4, and 8
- Proportion of patients achieving at least 1-point decrease in IGA at Week 8

All secondary endpoint based on the change from baseline will be assessed using an ANCOVA where the change from baseline will be the dependant variable and including the treatment group and site as fixed effects and baseline value as a covariate. In addition, ANCOVA will also be performed on the change from baseline at week 10 and on the change from Week 8 to Week 10.

All secondary endpoint based on categories will be analysed using a Cochran-Mantel-Haenszel test stratified by site and the p-value from this test will be presented along with frequency and percentage of subjects for each category.

All change and percent change values will be summarized using descriptive statistics, for each treatment group and visit. Proportion of subjects with no, 1-point, 2-point, 3-point, decrease/increase, will be presented at Week 8.

All statistical analyses will be done at each visit and using the ITT (primary analysis) and PP (supportive analysis) population. All the analyses will be done using observed values. Results collected during the early termination visit related to Week 8 and Week 10 will not be included. No sensitivity analysis will be done for missing values.

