7.7 Early termination visit

In the case the subject ends the study before completion, the procedures listed at Week 8 visit should be completed (section 7.5). Subject will also return two weeks later for the following Follow-up/Week 10 safety assessments:

- Concomitant medications
- Safety labs (only if there was a clinically significant change from baseline at the ET visit)
- Urine pregnancy test, if female of childbearing potential
- Vital signs
- Physical exam
- Adverse events

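### An early-termination assessment that replaces the Week 2 or Week 4 visit, inside that visit's window, is used at no visit in the secondary change-from-baseline analyses

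*SAP*

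**What the plan says.** Protocol 5.4 ties the early-termination evaluation to Week 8 but places it at the moment of withdrawal: "A complete final early termination (week 8) evaluation at the time of the subject's withdrawal should be made". On timing it adds: "Subjects who discontinue the study before week 8 visit will be asked to come for an early termination visit as soon as possible". Protocol 7.7 repeats the content: "In the case the subject ends the study before completion, the procedures listed at Week 8 visit should be completed". The Week 8 list in Protocol 7.5 contains every secondary efficacy measure: IGA, EASI, SCORAD with the pruritus VAS, POEM, DLQI and BSA, with TEWL at selected sites. The flow charts in both documents, and the SAP's mock visit table and listing, give Week 8 and early termination a single column. SAP 7.1 uses the same label when it describes non-completers as "subjects with an early termination visit at Week 8".

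For the secondary endpoints SAP 7.2 says three things. On the data basis: "All the analyses will be done using observed values". On withdrawn subjects, it then sets their last evaluation aside: "Results collected during the early termination visit related to Week 8 and Week 10 will not be included". On the gaps that this leaves, it says: "No sensitivity analysis will be done for missing values". SAP 7.3 applies the same ANCOVA to TEWL.

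The only rule close to visit assignment is in SAP 5.3. It covers two values recorded for the same visit and keeps the scheduled one. It does not say where an early-termination value belongs when no scheduled value exists.

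**The concern.** Suppose a subject's Day 28 attendance becomes the early-termination visit. The full efficacy battery is done on the Week 4 target day but recorded under Week 8. SAP 7.2 keeps it out of Week 8, which is reasonable because it is not a Week 8 measurement. Nothing brings it into Week 4. The value is collected, on schedule, and unused.

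This matters because withdrawal may be related to outcome. Subjects stop their atopic dermatitis treatment to enter (inclusion criterion 7), and Protocol 5.4 lists the need for another effective agent as a reason for discontinuation. The lost values may therefore come disproportionately from subjects doing badly, and SAP 7.2 plans no sensitivity analysis that would show the effect.

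There is also a consistency point. Protocol 14.2.2 promises observed data for the secondary endpoints, and an early-termination value is observed. SAP section 11, which lists additions to the protocol, does not mention the exclusion.

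**Working it through.** **1. Which values can be lost.** Protocol 7.3 sets Week 2 at Day 14 ± 2, so Days 12-16. Protocol 7.4 sets Week 4 at Day 28 ± 2, so Days 26-30. Each window is 5 days. There are four cases:

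- Scheduled visit attended, withdrawal later: the scheduled value is observed and stays in. Nothing is lost.
- Early-termination visit outside both windows: there is no on-schedule Week 2 or Week 4 value to lose.
- Early-termination visit inside a window, scheduled value also recorded: the scheduled value stands. Nothing is lost.
- Early-termination visit inside a window, in place of the scheduled visit: the value is used at no visit.

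Only the last case is a loss, and it costs each subject one visit. A subject whose early-termination visit replaces Week 4 keeps the Week 2 data.

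**2. Which comparisons are affected.** SAP 7.2 lists seven change-from-baseline endpoints: IGA, EASI, POEM, DLQI, SCORAD, VAS and BSA. At Weeks 2 and 4 that gives 7 × 2 = 14 ITT comparisons. The per-protocol analyses repeat them, and TEWL adds two visits at selected sites.

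**3. The plan's drop-out figure.** SAP section 4 gives 45 subjects (per group, as the total implies), 10% drop-out and 100 in total. 2 × 45 = 90, and 90 / (1 − 0.10) = 100, so the figure reproduces and implies 10 drop-outs.

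**4. Expected number lost.** The documents give no timing for withdrawals. Assume early-termination days are uniform over Days 1-53, the days before the Week 8 window opens on Day 54 (56 − 2), and that every in-window early-termination visit replaces the scheduled one. Then the expected loss per endpoint is D × 5/53 per window and D × 10/53 over both, for D drop-outs:

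| Drop-outs D | Per window | Both windows |
|---|---|---|
| 10 (planned) | 0.9 | 1.9 |
| 20 (assumed) | 1.9 | 3.8 |
| 30 (assumed) | 2.8 | 5.7 |

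With 10 drop-outs the limits are 0 (none in a window) and 10 (all in a window).

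**5. Effect on precision.** Losing m of 100 values at a visit multiplies the standard error by about √(100 / (100 − m)): 1.005 for m = 1, 1.010 for m = 2, 1.026 for m = 5 and 1.054 for m = 10.

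**6. Effect on the estimate, by illustration only.** Assume 50 placebo subjects, with those lost at Week 4 averaging an EASI change of +4 and the rest −4. With 1 lost, the full mean is (49 × −4 + 1 × 4) / 50 = −3.84 against −4.0 reported, a shift of 0.16. With 5 lost, it is (45 × −4 + 5 × 4) / 50 = −3.2, a shift of 0.8. On these assumptions, losses confined to placebo understate a drug benefit, losses confined to the active arm overstate it, and equal losses in both arms largely cancel.

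**The case against.** The strongest reply is that SAP 7.2 never says data are removed from Week 2 or Week 4. The words about Week 8 and Week 10 can be read as keeping early-termination results out of those two analyses only. That reading is fair, and a reader who infers an explicit exclusion from the earlier visits goes beyond the text. But the narrow reading does not place the values anywhere either. Combined with the Week 8 label and no study-day rule, it leaves the early visits to the programmer, and two programmers could produce different tables.

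Second, the protocol does not say that an early-termination visit replaces a scheduled visit that is due. That is correct, and it limits the point. A reader might infer that everyone who withdraws around Week 2 or Week 4 loses data; the documents do not support that.

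Third, the consequence is small. The primary analysis counts non-completers as non-responders, and the supportive LOCF analysis in SAP 7.1 uses the early-termination IGA. SAP 6.1 compares discontinuation and its reasons by arm, and the efficacy data are listed, so a problem could be seen afterwards. All of this stands. It lowers the weight of the point without closing the gap.

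Fourth, an early-termination value may follow the start of another treatment. Whether it should count at Week 4 is then a choice of estimand. That also stands, and the rule needs to address it.

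**Conclusion.** The gap is real but narrow. As written, an early-termination assessment inside the Week 2 or Week 4 window, made in place of the scheduled visit, is used at no visit in the secondary change-from-baseline analyses. At the planned drop-out, about 2 values per endpoint over both visits would be affected, with a possible range of 0 to 10. The estimate of 2 rests on uniform timing and on every in-window early-termination visit replacing the scheduled one; clustering of withdrawals at visits would raise it. The cost in precision is about 0.5% to 1% of the standard error at a visit for 1 or 2 lost values.

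A reader might infer a loss of several percent of the data, or a bias as large as the 0.8-point EASI illustration. The documents support neither. That illustration puts all 5 lost subjects in one arm at one visit, each set worsening on average. The size and direction of any bias depend on drop-out timing and arm imbalance, which are not given. The change is worth making because it is cheap and recovers collected, possibly informative data.

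**What to change.** Add to SAP 7.2, before database lock and unblinding, a rule to this effect: *When no scheduled Week 2 or Week 4 value exists, an early-termination efficacy assessment falling within the protocol window for that visit (Day 14 ± 2 or Day 28 ± 2) is analysed at that visit; early-termination data remain excluded from Week 8 and Week 10.*

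The rule should also state how values measured after the start of another atopic dermatitis treatment are handled in the analysis. Keeping to the protocol's own ± 2 days limits the recovery to values that really were on schedule; wider windows would admit values well off the target day. TEWL should follow the same rule through SAP 7.3.

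The cost is one SAP sentence and one programming step. The downside is that some assigned values may be taken shortly after the last dose.
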